3.2.12 Interim analysis

An interim analysis will be performed after the first 30 patients enrolled have completed at least 4 cycles of treatment with LDK378 or have discontinued earlier. The interim analysis will focus on full pharmacokinetics profile, safety and preliminary efficacy data listed as below. For details on the extent of interim analysis, please refer to appendix 1 [List of output for interim analysis](#)

- Pharmacokinetics: A statistical analysis will be performed on the PK data. Plasma concentration of LDK378 and PK parameters will be summarized and listed.
- Safety: all adverse events observed by the data cutoff date will be summarized and listed. Separate summaries will be provided for SAE and death, respectively. Abnormal results on laboratory assessment and ECG will be presented and listed in detail.
- Efficacy: ORR observed by the data cutoff date will be estimated with corresponding binomial exact 95% CI.

3.3 Section 9.7.2 Sample size calculation

Overall approximately 100 patients will be enrolled. This sample size was deemed to be adequate to assess safety, and tolerability and demonstrate the anti-tumor activity of LDK378 in Chinese patients.

The first 15 patients being enrolled in the phase I component will have a 5 -day PK run-in period so to obtain approximately 12 evaluable PK profiles.

3.4 Power for analysis of key secondary variables

With a total of 100 patients, if the observed ORR (key secondary endpoint) is 45% (45 responders in 100 treated patients), this will results in an exact binomial 90% CI of [36.5%, 53.7%].

4 Appendix 16.1.9 of CSR- Documentation of statistical method

4.1 Statistical methods

The statistical methodologies used are described and discussed in Section 9.7 of the CSR. In Section 16.1.9, details of the statistical methods and their justification are provided for the statistical reviewers.

All analyses will be performed using SAS® Version 9.4 (or later version if available at time of database lock).

4.1.1 Difference between SAP and protocol

Not applicable.

4.1.2 Handling of missing or partial dates

For patients not known to have died prior to the cut-off date:

- All events with start date before or on the cut-off date, and with end date missing or after the cut-off date or after the date of withdrawal of informed consent will be reported as “continuing”.
- This approach applies, in particular, to AEs and concomitant medication report. For these events, the end date will not be imputed and therefore will not appear in the listings.

For patients known to have died prior to or on the cut-off date:

- All events with start date before or on the cut-off date, and with end date missing or after the cut-off date or after the date of withdrawal of informed consent will have the end date imputed to the death date.
- This approach applies, in particular, to AEs and concomitant medication report. For these events, the imputed end date will not appear in the listings.

If imputation of an end date is required for a specific analysis (e.g. for a dose administration record with missing end date or last date of study treatment after the cut-off date), the end date will be imputed to the min (cut-off date, death date, withdrawal of informed consent date) for the purpose of calculating duration of exposure to study drug and dose intensity. The imputed date will be displayed and flagged in the listings.

4.1.2.1 AE date imputation

Date imputation is the creation of a new, complete date from a partial one according to an agreed and acceptable algorithm. Missing date for AE will be handled according to rules specified below. A partial date is simply an incomplete date e.g. DDOCT2001: the days are missing from this DDMMYY date.

Partial AE start dates, if left partial, would ultimately mean the following

It would not be possible to place the AE in time.

Therefore the treatment/dosage at the time of the event would be unknown.

Therefore the event could not be reported/summarized appropriately – if at all.

Therefore it is important to perform date imputation to ensure that as many data events are represented as correctly as possible. Of course partial and/or missing dates should *also* be caught as edit checks and passed back to the investigator for resolution.

There **will be no** attempt to impute the following:

- **Missing** AE start dates
- AE start dates **missing the year**
- Partial/missing AE **end dates**

The following [Table 4-1](#) explains the abbreviations used.

Table 4-1 AE/treatment date abbreviations

	Day	Month	Year
Partial Adverse Event Start Date	<not used>	AEM	AEY
Treatment Start Date (TRTSTD)	<not used>	TRTM	TRTY

The following matrix [Table 4-2](#) describes the possible combinations and their associated imputations. In the light grey boxes the upper text indicates the imputation and the lower text the relationship of the AE start date to the treatment start date (TRTSTD).

Table 4-2 AE partial date imputation algorithm

	AEM MISSING	AEM < TRTM	AEM = TRTM	AEM > TRTM
AEY MISSING	NC Uncertain	NC Uncertain	NC Uncertain	NC Uncertain
AEY < TRTY	(D) Before TRTSTD	(C) Before TRTSTD	(C) Before TRTSTD	(C) Before TRTSTD
AEY = TRTY	(B) Uncertain	(C) Before TRTSTD	(B) Uncertain	(A) After TRTSTD
AEY > TRTY	(E) After TRTSTD	(A) After TRTSTD	(A) After TRTSTD	(A) After TRTSTD

The following [Table 4-3](#) is the legend to the above table.

Table 4-3 AE/treatment date relationship and imputation legend

Relationship	
Before TRTSTD	Indicates AE start date prior to Treatment Start Date
After TRTSTD	Indicates AE start date after Treatment Start Date
Uncertain	Insufficient to determine the relationship of AE start date to Treatment Start Date
Imputation Calculation	
NC / Blank	No convention/imputation
(A)	01MONYYYY
(B)	TRTSTD+1
(C)	15MONYYYY
(D)	01JULYYYY
(E)	01JANYYYY

The following [Table 4-4](#) gives a few examples.

Table 4-4 AE imputation example scenarios

Partial AE start date	Treatment start date	Relationship	Imputation Calculation	Imputed Date
12mmYYYY	20OCT2001	Uncertain	NC	<blank>
ddmmm2000	20OCT2001	Before	(D)	01JUL2000
ddmmm2002	20OCT2001	After	(E)	01JAN2002
ddmmm2001	20OCT2001	Uncertain	(B)	21OCT2001
ddSEP2001	20OCT2001	Before	(C)	15SEP2001
ddOCT2001	20OCT2001	Uncertain	(B)	21OCT2001
ddNOV2001	20OCT2001	After	(A)	01NOV2001

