4.1 Description of study design

This is a phase I/II, open-label, multi-center study in which the PK, safety, tolerability and efficacy of LDK378 will be assessed in adult Chinese patients with locally advanced or metastatic NSCLC harboring a confirmed ALK rearrangement, defined as positive using the FDA approved Vysis ALK Break Apart FISH Probe Kit (Abbott Molecular Inc.) test and scoring algorithm (including positivity criteria) or positive as assessed by the CFDA approved immunohistochemistry (IHC) test (Ventana Medical Systems, Inc) using rabbit monoclonal primary antibody assay (D5F3) and associated scoring algorithm.

If documentation of ALK rearrangement is not available as described above, a test to confirm ALK rearrangement must be performed using an archival tumor obtained at or since the time of diagnosis or a new tumor biopsy obtained prior to the first LDK378 dose. The test will be performed at a Novartis designated central laboratory (by IHC test using rabbit monoclonal primary antibody assay (D5F3), Ventana Medical Systems, Inc). Patients must wait for the result of the ALK rearrangement status before initiating treatment with LDK378.

Patients must have demonstrated progression during or after crizotinib treatment whether or not previously treated with cytotoxic chemotherapy and have no available ALK-targeted treatment options.

Overall approximately 100 patients with locally advanced or metastatic NSCLC which harbor ALK -rearrangement will be enrolled in the study. Patients will have a screening period, a treatment period, an end of treatment (EOT) assessment and a follow up period.

The study begins with a screening period, up to and including 28 days prior to the first dose of LDK378, to assess eligibility.

The first 15 enrolled patients will enter a 5-day PK run-in period during the phase I component of this study. The phase II component of the study will start on Cycle 1 Day 1 for all enrolled patients.

The first 15 patients to be enrolled in the phase I component of the study will have PK sampling over 120-hour during the 5-day PK run-in period following a single oral dose at 750 mg. This will be done in order to characterize the PK profile, safety and tolerability of LDK378 after single dosing in this population.

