8.1 Adverse events

8.1.1 Definitions and reporting

An adverse event is defined as the appearance of (or worsening of any pre-existing) undesirable sign(s), symptom(s), or medical condition(s) that occur after patient's signed informed consent has been obtained.

Abnormal laboratory values or test results occurring after informed consent constitute adverse events only if they induce clinical signs or symptoms, are considered clinically significant, require therapy (e.g., hematologic abnormality that requires transfusion or hematological stem cell support), or require changes in study medication(s).

Adverse events that begin or worsen after informed consent should be recorded in the Adverse Events CRF. Conditions that were already present at the time of informed consent should be recorded in the Medical History page of the patient's CRF. Adverse event monitoring should be continued for at least 30 days (or 5 half-lives, whichever is longer) following the last dose of study treatment. Adverse events (including lab abnormalities that constitute AEs) should be described using a diagnosis whenever possible, rather than individual underlying signs and symptoms. When a clear diagnosis cannot be identified, each sign or symptom should be reported as a separate Adverse Event.

Adverse events will be assessed according to the Common Terminology Criteria for Adverse Events (CTCAE) version 4.03 (dated 14 June 2010). If CTCAE grading does not exist for an adverse event, the severity of mild, moderate, severe, and life-threatening, corresponding to Grades 1 - 4, will be used. CTCAE Grade 5 (death) will not be used in this study; rather, information about deaths will be collected through a Death eCRF.

Abnormal laboratory values or test results occurring after signing the ICF constitute adverse events only if they induce clinical signs and symptoms, or require therapy, (e.g., any hematologic abnormality that requires transfusion of hematological stem cell support) or changes in medication(s) are considered clinical significant and should be recorded on the Adverse Event eCRF under signs, symptoms or diagnosis associated with them. In addition, isolated abnormal laboratory values that are considered clinical significant (e.g. cause study discontinuation or constitute in and of itself a Serious Adverse Event) should be recorded on the Adverse Events eCRF.

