The occurrence of adverse events should be sought by non-directive questioning of the patient (subject) during the screening process after signing informed consent and at each visit during the study. Adverse events also may be detected when they are volunteered by the patient (subject) during the screening process or between visits, or through physical examination, laboratory test, or other assessments. As far as possible, each adverse event should be evaluated to determine:

- The severity grade (CTCAE Grade 1-4)
- Its duration (Start and end dates)
- Its relationship to the study treatment (Reasonable possibility that AE is related: No, Yes)
- Action taken with respect to study or investigational treatment (none, dose adjusted, temporarily interrupted, permanently discontinued, unknown, not applicable)
- Whether medication or therapy was given (no concomitant medication/non-drug therapy, concomitant medication/non-drug therapy)
- Outcome (not recovered/not resolved, recovered/resolved, recovering/resolving, recovered/resolved with sequelae, fatal, unknown)
- Whether it is serious, where a serious adverse event (SAE) is defined as in [Section 8.2.1](#)

All adverse events should be treated appropriately. If a concomitant medication or non-drug therapy is given, this action should be recorded on the Adverse Event CRF.

Once an adverse event is detected, it should be followed until its resolution or until it is judged to be permanent, and assessment should be made at each visit (or more frequently, if necessary) of any changes in severity, the suspected relationship to the study treatment, the interventions required to treat it, and the outcome.

Progression of malignancy (including fatal outcomes), if documented by use of appropriate method (for example, as per RECIST criteria for solid tumors or as per Cheson's guidelines for hematological malignancies), should not be reported as a serious adverse event.

Adverse events separate from the progression of malignancy (example, deep vein thrombosis at the time of progression or hemoptysis concurrent with finding of disease progression) will be reported as per usual guidelines used for such events with proper attribution regarding relatedness to the drug.

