3.2.9 Safety evaluation

All safety analyses will be performed based on the Safety Set.

Grouping for the analyses

Safety summaries will include data from the following three mutually exclusive segments:

- Pre-treatment period: from day of patient's informed consent to the day before first dose of study treatment.
- On-treatment period:
 - For discontinued patients, from day of first dose of study drug to 30 days after last dose of study drug
 - For ongoing patients, from day of first dose of study drug to the data cut-off date
- Post-treatment period: starting at day 31 after last dose of study drug

The safety summary tables will include only assessments during the on-treatment period, unless otherwise specified. For select items, shift tables or change from baseline summaries generated

for laboratory, ECG, vital signs and change score generation may use data from pre-treatment period for baseline calculations.

All data, regardless of observation period, will be listed and assessments collected in pre-treatment and post-treatment period will be flagged in all the listings.

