3.2.9.1 Adverse events (AEs)

Summary tables for AEs will include only AEs observed during the on-treatment period. AEs will be coded using MedDRA using the latest version available prior to clinical database lock and will be graded using Common Terminology Criteria for Adverse Events (CTCAE) version 4.03. If CTCAE grading does not exist for an AE, grades 1, 2, 3, or 4 corresponding to the severity of mild, moderate, severe, and life-threatening, respectively, will be used. CTCAE grade 5 (death) will not be used in this study; rather, this information will be collected on the “End of Treatment Phase Disposition”, “Post-treatment Phase Completion” or “Death” eCRF pages.

All AE summaries will be summarized (frequency counts and percentages) by SOC and/or PT, maximum severity grades (based on CTCAE grades), and relation to study drug except where otherwise noted. A patient with multiple CTC grades for an AE will be summarized under the maximum CTC grade recorded for the event.

Deaths reportable as SAEs and non-fatal SAEs will be listed by patient. AEs leading to study discontinuation and AEs requiring dose adjustment or interruption will be listed separately.

The following AE summaries will be produced:

- AEs regardless of study drug relationship
- AEs suspected to be study drug related
- All deaths, by primary SOC and PT
- On-treatment deaths, by primary SOC and PT
- SAEs regardless of study drug relationship
- SAEs suspected to be study drug related
- AEs associated with discontinuation of study drug
- AEs requiring dose adjustment or study drug interruption
- AEs requiring dose adjustment
- AEs requiring study drug interruption
- AEs requiring concomitant medication or non-drug therapy
- AEs excluding SAEs
- On-treatment deaths and serious adverse events by primary SOC and PT
- Non-serious adverse events (threshold = 5%) by primary SOC and PT

Adverse events of special interest

AESIs are defined as AEs within the following categories/ groupings of PTs:

- Hepatotoxicity
- Interstitial lung disease/Pneumonitis

CONFIDENTIAL - For Business Use Only

- QTc prolongation
- Hyperglycemia
- Bradycardia
- GI toxicity (including nausea, diarrhea, vomiting)
- Pancreatitis (including lipase or amylase increases)

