4.1.2.4 Incomplete date for anti-neoplastic therapies

Prior therapies

Start date:

The same rule which is applied to the imputation of AE/concomitant medication start date will be used with the exception that for scenario (B) will be replaced to be 'start date of treatment -1'.

End date:

Imputed date = min (start date of study treatment, last day of the month), if day is missing;

Imputed date = min (start date of study treatment, 31DEC), if month and day are missing.

If the end date is not missing and the imputed start date is after the end date, use the end date as the imputed start date.

If both the start date and the end date are imputed and if the imputed start date is after the imputed end date, use the imputed end date as the imputation for the start date.

Post therapies

Start date:

Imputed date = max (last date of study treatment + 1, first day of the month), if day is missing;

Imputed date = max (last date of study treatment + 1, 01JAN), if day and month are missing.

End date: No imputation

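### SAP 4.1.2.1 rule (B) ignores a known AE end date, so an event that ended before first dose can be given a start after its end and counted as on-treatment

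*SAP*

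**What the plan says.** Tables 4-1 to 4-3 in SAP 4.1.2.1 take three inputs: AE start month, AE start year and treatment start date (TRTSTD). When the AE year equals the treatment year and the AE month is equal or missing, the cell is marked Uncertain, defined as "Insufficient to determine the relationship of AE start date to Treatment Start Date". Rule (B) then gives TRTSTD+1. The AE end date is not an input. The section mentions end dates only to say that partial or missing ones are not imputed. Its one safeguard is that partial or missing dates should "be caught as edit checks and passed back to the investigator for resolution".

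SAP 4.1.2.2 applies the same convention to concomitant medication start dates.

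SAP 4.1.2.4, for prior antineoplastic therapies, does use the end date: "If the end date is not missing and the imputed start date is after the end date, use the end date as the imputed" start.

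For the safety analysis, SAP 3.2.9 defines the on-treatment period: "For discontinued patients, from day of first dose of study drug to 30 days after last dose of study drug" (to data cut-off for ongoing patients). SAP 3.2.9.1 adds: "Summary tables for AEs will include only AEs observed during the on-treatment period".

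**The concern.** Pre-treatment AEs with a recorded end are part of the planned data. Protocol 8.1.1 says: "Adverse events that begin or worsen after informed consent should be recorded in the Adverse Events CRF". The same section has each event evaluated for "Its duration (Start and end dates"). Protocol 4.1 states: "The study begins with a screening period, up to and including 28 days prior to the first dose of LDK378, to assess eligibility". An AE can therefore start and end in screening, in the calendar month of first dose.

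If the start day is lost but the end date is complete and precedes first dose, the order of event and treatment is known. Rule (B) still treats it as unknown and dates the event after first dose. The event then starts after it has ended, and appears to have arisen on the study drug. Safety and tolerability form one of the two primary objectives (SAP 2.1), and the AE tables are their main output. For medications, a drug stopped before first dose can appear as one started on study.

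**Working it through.** **Inputs.** Imputation codes from SAP Table 4-3: (A) first of the recorded month, (B) TRTSTD+1, (C) 15th of the recorded month, (D) 1 July, (E) 1 January. Cells from Table 4-2. TRTSTD = 20OCT2001 from Table 4-4.

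**1. Reproduce Table 4-4.** Applying Tables 4-2 and 4-3 to its seven scenarios gives: year missing, blank; 2000, (D) 01JUL2000; 2002, (E) 01JAN2002; 2001, (B) 21OCT2001; SEP2001, (C) 15SEP2001; OCT2001, (B) 21OCT2001; NOV2001, (A) 01NOV2001. All seven match the SAP.

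**2. Add a known end date before first dose.** The cap is: imputed start = min(rule date, known end date).

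| Recorded start | Known end | Start under (B) | Start minus end | Start with cap |
|---|---|---|---|---|
| ddOCT2001 | 05OCT2001 | 21OCT2001 | 16 days | 05OCT2001 |
| ddOCT2001 | 10OCT2001 | 21OCT2001 | 11 days | 10OCT2001 |
| ddmmm2001 | 10OCT2001 | 21OCT2001 | 11 days | 10OCT2001 |
| ddOCT2001 | 19OCT2001 | 21OCT2001 | 2 days | 19OCT2001 |

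In every row the present rule puts the start in the on-treatment period, and the cap moves it to pre-treatment.

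**3. Which codes can do this.** Only (B). Codes (C) and (D) sit in cells already marked as before treatment and give dates before treatment. Codes (A) and (E) apply only when the start is already known to be after treatment start.

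**4. How often a partial screening start reaches (B).** The documents give no count of partial dates, so this is conditional on the start being partial. Assume first-dose dates spread evenly over a 365-day year and AE starts spread evenly over the 28 days before, giving 365 × 28 = 10,220 pairs.

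- Day missing: for first dose on day d of the month, min(d − 1, 28) of the 28 days share its month. Summed over d, this is 462 for a 31-day month, 434 for a 30-day month and 378 for February. Total: 7 × 462 + 4 × 434 + 378 = 5,348, and 5,348/10,220 = 52%. It ranges from 0% for first dose on the 1st to 100% on the 29th or later.
- Day and month missing: the days must share the calendar year. The first 29 days of the year contribute 0 + 1 + … + 28 = 406, and the other 336 contribute 28 each, or 9,408. Total: 9,814/10,220 = 96%.

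**5. Weight of one event.** The protocol's Amendment 3 rationale gives 103 treated patients, and 1/103 = 0.97%. The tables count patients, so a row changes only if that patient has no other on-treatment event of that term. SAP 3.2.9.1 includes a non-serious AE table with a 5% threshold: 5/103 = 4.9% and 6/103 = 5.8%, so one patient can decide whether a term appears.

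**6. Medications.** A drug with start ddmmm2001 and end 10OCT2001 also gets 21OCT2001. SAP 3.2.6 then includes it as starting after treatment start. It also escapes the listing flag for items that both start and end before treatment.

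**The case against.** The strongest case against is that this is narrow and leans in a safe direction. Three things must coincide: a partial start in an Uncertain cell, an end date that precedes first dose, and an unresolved query. Protocol 9.3 and 9.4 add automatic checks, site queries and verification before lock. The error can only over-count on-treatment AEs, and the trial is single-arm with no formal hypothesis test (Protocol 10.10). All of this stands and limits the size. It does not remove the gap, because imputation exists for dates that queries fail to recover, and over-counting is not useful caution when the order of events is known.

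A second objection is that the SAP never states outright that on-treatment status follows the start date. That is true. But 4.1.2.1 gives placing the AE in time relative to treatment as the purpose of imputation, and 3.1.2 uses the AE start date to decide inclusion at the cut-off. The start-date reading is the natural one.

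Third, the cap in 4.1.2.4 sits beside a different rule (B), one day before treatment, and beside imputed end dates, so it is not an exact parallel. That is fair, but the sentence quoted from 4.1.2.4 covers end dates that were recorded rather than imputed.

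A reader might infer three stronger things that the documents do not support. One is that impossible durations reach the safety tables. SAP 3.2.9.1 specifies no AE duration summary, so these would show only in listings. Another is that rule (C) misclassifies events too. It can give a start after the end (ddSEP2001 with end 05SEP2001 gives 15SEP2001, 10 days late), but the event stays pre-treatment. The third is that 52% or 96% of such events are wrong. Those are shares of partial screening starts sent to (B), under assumed even spread, and not error rates.

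**Conclusion.** The point holds in limited form. For an AE or medication whose partial start date falls in an Uncertain cell and whose recorded end precedes first dose, rule (B) produces a start later than the end. On the start-date reading of SAP 3.2.9 and 3.2.9.1, it places the AE on-treatment. This is a stated rule giving a wrong classification, so it is wrong as written for those records. TRTSTD+1 remains a reasonable choice where the end date is missing or falls on or after first dose, and records with complete start dates are untouched.

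The number of affected records cannot be computed from the documents and is probably small. This is a minor correction that would be good to make. It does not threaten the safety conclusions.

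**What to change.** Add to SAP 4.1.2.1 and 4.1.2.2 the check already in 4.1.2.4: if a complete end date is earlier than the imputed start date, use the end date as the start date. An event ending on the day of first dose would then start that day and stay on-treatment, while one ending earlier becomes pre-treatment.

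That alone misses partial end dates. For example, start ddmmm2001, end ddSEP2001 and first dose 20OCT2001 would still give 21OCT2001. So add a second sentence: where the month and year of a partial end date are clearly before first dose, class the event or medication as pre-treatment.

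It would also help to say in 3.2.9 that on-treatment status is assigned from the start date, imputed where necessary.

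The cost is two or three sentences and a few lines of code. No data collection changes.
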